In addition to the above-mentioned 3 intercurrent events, the COVID-19 pandemic makes it appropriate to introduce an attribute of individual data points that influences their handling in some of the estimands:

- **Missing data due to the COVID-19 pandemic:**

This attribute is related to a missing data point (assessment) that is accounted for in a given estimand analysis. It is assigned to each data point that is missing due to the COVID-19 pandemic as outlined in section 14.3.1.

An overview of how the applied estimands handle the intercurrent events and missing data is presented below (Panel 13).

Panel 13: Handling of intercurrent events and missing data in the primary analysis of estimands

	Binary endpoints				Continuous endpoints			
	Missing or observed data	COVID-19 modified composite	Composite	treatment policy	hypothetical	hypothetical	treatment policy	COVID-19 modified composite
First prior intercurrent event								
Rescue treatment	Missing data	Non-response	Non-response	Event ignored ¹	MI	Not used	Event ignored ¹	WOCF
	Observed data	Non-response	Non-response	Event ignored ¹	MI	Not used	Event ignored ¹	WOCF
Permanent discontinuation of IMP	Missing data	Non-response	Non-response	MI – discontinued	MI	Not used	MI – discontinued	WOCF
	Observed data	Non-response	Non-response	Used	MI	Not used	Used	WOCF
Subject-onset of the COVID-19 pandemic	Missing data	MI	Event ignored ²	MI – not discontinued	MI	Not used	MI – not discontinued	MI
	Observed data	MI	Event ignored ²	MI – not discontinued	MI	Not used	MI – not discontinued	MI
No prior intercurrent event	Missing data not due to the COVID-19 pandemic	Non-response	Non-response	MI – not discontinued	MI	Not used	MI – not discontinued	MI
	Missing data due to the COVID-19 pandemic	MI	Non-response	MI – not discontinued	MI	Not used	MI – not discontinued	MI
	Observed data	Used	Used	Used	Used	Used	Used	Used

Abbreviations: COVID-19 = Coronavirus Disease 2019; IMP = investigational medicinal product; MI = multiple imputation; MI – discontinued = MI method using only retrieved data at Week 16 / Week 26 from discontinued subjects; MI – not discontinued = stepwise MI method using data from not discontinued subjects.; WOCF = Worst observation carried forward.

- 1) Rescue treatment is ignored as an intercurrent event in the treatment policy estimands.
- 2) Subject-onset of the COVID-19 pandemic is ignored as an intercurrent event in the composite estimand.

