14.3.8.3 Tertiary estimand: ‘treatment policy’

The tertiary estimand for the primary endpoint will be:

- Treatment difference in response rate of EASI75 after 16 weeks between tralokinumab+TCS and placebo+TCS regardless of rescue treatment and IMP discontinuation, as if the COVID-19 pandemic did not happen

The tertiary estimand assesses the average difference in response rates, resulting from initiation of a treatment regimen with tralokinumab+TCS and rescue treatment as compared to a treatment regimen with placebo+TCS and rescue treatment.

Primary analysis for the tertiary estimand

Data retrieved at Week 16 for subjects who prior to Week 16 have permanently discontinued IMP for other reasons than the COVID-19 pandemic will be included in the analysis.

For subjects who have subject-onset of the COVID-19 pandemic prior to Week 16 and prior to any permanent discontinuation of IMP not due to the COVID-19 pandemic, any observed data from these subjects will be ignored and treated as missing in the same manner as missing data from not discontinued subjects in the analysis ([Panel 13](#)).

Imputation of missing data at Week 16 will be done using multiple imputations within 4 groups defined according to randomised treatment group and whether or not subjects have permanently discontinued IMP prior to Week 16. Within a given treatment group, retrieved data from discontinued subjects will be used to impute missing data for other discontinued subjects. Similarly, the available data from not discontinued subjects will be used to impute data for such subjects where the Week 16 value is missing/treated as missing.

For not discontinued subjects, the stepwise multiple imputations procedure will be conducted in the same way, using the same seeds, as specified for the primary analysis of the quaternary ‘hypothetical’ estimand described in [Section 14.3.8.4](#).

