For discontinued subjects, it is expected that the number of subjects with retrieved data at Week 16 will be too small to facilitate the same imputation model as mentioned above. Consequently, a separate imputation model at Week 16 with only prior CSA use (yes/no) and baseline disease effects (IGA as a factor and EASI as a covariate) will be applied for discontinued subjects. Some factors may have to be omitted, depending on the observed data, e.g. if all subjects have the same baseline disease severity. In that case the preferred order of elimination of the effects from the imputation model will be: prior CSA use and baseline disease effects (seed=12576546).

The imputed datasets will be analysed in the same way as specified for the primary analysis of the quaternary ‘hypothetical’ estimand in [Section 14.3.8.4](#).

Sensitivity analyses for the tertiary estimand

Rather than imputing Week 16 data as described in the primary analysis of the tertiary estimand, missing observations not caused by subject-onset of the COVID-19 pandemic or not missing due to the COVID-19 pandemic, will be imputed as ‘non-responders’. The assumption reflects that discontinued subjects without retrieved data at Week 16 are more likely to be non-responders than resembling discontinued subjects with retrieved data at Week 16. Missing observations due to either subject-onset of the COVID-19 pandemic or missing due to the COVID-19 pandemic, will be imputed as described in the primary analysis of the tertiary estimand.

In case the number of discontinued subjects attending the nominal Week 16 visit is too low to fit the imputation model in the primary analysis of the tertiary estimand, the sensitivity analysis will become the primary analysis of the tertiary ‘treatment policy’ estimand.

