The stratification variables used will be the same as the ones used in the corresponding analyses and will be specified as strata to the conditional logistic regression model. If a stratification variable (prior CSA use [yes/no] or baseline disease severity [IGA 3 or 4]) is the subject of a subgroup analysis, then the variable will be omitted from the stratification for that analysis. The p-value of the interaction term between treatment and the subgroup will be reported as the interaction test outcome. Subgroup analyses will be performed for the following endpoints:

- EASI75 at Week 16
- EASI75 at Week 26
- Reduction of Worst Daily Pruritus NRS (weekly average) of at least 4 from baseline to Week 16.
- Reduction of Worst Daily Pruritus NRS (weekly average) of at least 4 from baseline to Week 26
- IGA score of 0 or 1 at Week 16
- IGA score of 0 or 1 at Week 26

The binary endpoint IGA 0/1 will be analysed as described for the primary endpoint using all 4 estimands with the modification that the following imputation algorithm will be used for the primary, tertiary, and quaternary estimands.

IGA 0/1 responder imputation

Imputation of missing binary IGA 0/1 data at Week 16 and Week 26 will be done using multiple imputations of the underlying 5-point IGA values within the 2 groups defined according to randomised treatment group assuming that data is MAR within each group.

1. In each group, intermittent missing values will be imputed using last observation carried forward (LOCF) to obtain a monotone missing data pattern.

2. An ordinal logistic regression model assuming proportional odds will be fitted to the IGA value at Week 2. The model will include effects of prior CSA use (yes/no) and baseline disease severity (IGA 3 or 4) as factors. The estimated parameters, and their variances, will be used to impute missing IGA values at Week 2. 100 copies of the dataset will be generated (seed=37649846).
3. For each of the 100 copies of the dataset, missing values at Week 4 will be imputed in the same way as for Week 2. The imputations will be based on a proportional odds logistic regression model with effects of prior CSA use, and baseline disease severity together with the IGA value at Week 2 as factors. The estimated parameters, and their variances, will be used to impute missing values at Week 4.

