#### Secondary endpoints IGA 0/1

For imputation of IGA values, the LIKELIHOOD=AUGMENT option will be used (1).

For imputation of IGA values, it may occur that the observed data from which the imputation model is fitted does not contain all levels of the IGA predictors necessary for the imputation. Imputation will be performed within treatment groups at each visit. E.g. if at a visit within one treatment group, the IGA values (0,1,2,3) for each level have 2 or more observed values but the IGA value of 4 only has 1 or less, the imputation model will not be able to predict for IGA

values of 4 at that specific visit. I.e. categories can be combined at a visit for one group, but not the other. To avoid this situation, in this specific example IGA values of 3 and 4 will be combined into a single category prior to the imputation. In general, if this situation arises, IGA categories will be combined into a single category at the specific visit for the purpose of the imputation, according to the rules in [Table 1](#).

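### IGA 0/1 under treatment policy: a 2-group imputation is assigned to an estimand that elsewhere requires 4 groups, and no IGA model is given for discontinued subjects

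*Protocol*

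**What the plan says.** Protocol 14.3.9 analyses IGA 0/1 like the primary endpoint under all four estimands, with one modification: "the following imputation algorithm will be used for the primary, tertiary, and quaternary estimands". That algorithm works by "using multiple imputations of the underlying 5-point IGA values within the 2 groups defined according to randomised treatment group" and assumes MAR within each arm. It fills intermittent gaps by LOCF, then fits a proportional-odds model visit by visit to Week 16 or 26, using prior CSA use, baseline severity and up to two preceding IGA values.

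For the primary endpoint, the treatment-policy section (14.3.8.3) uses "multiple imputations within 4 groups defined according to randomised treatment group and whether or not subjects have permanently discontinued IMP prior to Week 16". Within an arm, "retrieved data from discontinued subjects will be used to impute missing data for other discontinued subjects", through a separate smaller model at Week 16. The stepwise procedure is borrowed only for subjects who have not discontinued. Panel 13 covers binary endpoints without excepting IGA. For missing data after discontinuation it prescribes MI – discontinued, defined as "MI method using only retrieved data at Week 16 / Week 26 from discontinued subjects".

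SAP 6.6.3.1 carries the treatment-policy rules of SAP 6.6.2 over to the binary secondary endpoints. One of those rules is a fallback: with two or fewer observed values among discontinued subjects in each arm, the sensitivity analysis becomes primary, and missing data unrelated to COVID-19 count as non-response (Protocol 14.3.8.3). SAP 6.6.4 adds technical detail on IGA imputation and does not mention discontinuation status.

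**The concern.** Treatment policy asks what happens regardless of discontinuation, so a missing off-drug outcome should be imputed from off-drug outcomes. A model fitted to the whole arm draws mostly on subjects still receiving IMP. After discontinuation, Panel 6 schedules only early termination, nominal Week 16 and 26, and follow-up visits, so the visit-by-visit chain contains few off-drug values at intermediate visits.

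IGA is the exception among the endpoints. EASI75 at Week 26 changes only the time horizon, pruritus changes only the score used in the imputation model, and SCORAD and DLQI under treatment policy (14.3.9.2) use four groups.

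At stake are the IGA 0/1 treatment-policy estimates at Weeks 16 and 26 and the subgroup analyses planned on the tertiary estimand. The programmer has to choose between two different assumptions. If the 2-group rule is combined with the fallback, there is also a jump: with two retrieved values per arm, missing off-drug subjects are non-responders, and with three they are imputed largely from on-drug subjects.

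**Working it through.** **Texts side by side**

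- Groups: 14.3.9 (IGA) has two, by arm; 14.3.8.3 has four, arm by discontinuation.
- Donors for a discontinued subject: 14.3.9 uses the whole arm; 14.3.8.3 and Panel 13 use retrieved discontinued subjects only.
- Model for discontinued subjects: given for EASI in 14.3.8.3 and for SCORAD/DLQI in 14.3.9.2; none for IGA in either document.

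The plan gives no figure on this point, so there is none to reproduce. Its power statement for EASI75 (99%) recalculates to 99.5% with 125 per arm at 40% vs 15%, but has no bearing here.

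**Size, by a simple mixture**

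Inputs from the documents: 250 subjects randomised 1:1, so 125 per arm; phase 2b Week 12 IGA 0/1 of 26% vs 12% (Protocol 5.2), used here as on-drug rates. Assumptions, because the documents give none: share discontinued D = 5%, 10% or 20%, equal in both arms; share of those with retrieved data r = 20% or 50%; a common off-drug rate q between 0 and 12%.

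- Share missing off drug: m = D(1 − r)
- On-drug share of donors under two groups: w = (1 − D) / (1 − D + Dr)
- Imputed rate: w × on + (1 − w) × q under two groups; q under four
- Arm-level shift: m × w × (on − q)
- Shift in the risk difference: m × w × [(26 − q) − (12 − q)] = m × w × 14 points, so the common q cancels

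| D | r | Retrieved per arm (125·D·r) | m | w | Shift in difference (points) |
|---|---|---|---|---|---|
| 5% | 50% | 3.1 | 0.025 | 0.974 | 0.34 |
| 5% | 20% | 1.25 | 0.040 | 0.990 | 0.55 |
| 10% | 50% | 6.25 | 0.050 | 0.947 | 0.66 |
| 10% | 20% | 2.5 | 0.080 | 0.978 | 1.10 |
| 20% | 50% | 12.5 | 0.100 | 0.889 | 1.24 |
| 20% | 20% | 5 | 0.160 | 0.952 | 2.13 |

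Donors are 89% to 99% on-drug. A missing off-drug tralokinumab subject is imputed as a responder with probability about 23% (0.889 × 26%, q = 0) to 26%, against the assumed 0 to 12%. At D = 20%, r = 20%, q = 0, the four-group difference is 0.8 × 14 = 11.2 points and the two-group difference is 11.2 + 2.1 = 13.3. The tralokinumab arm alone then shifts by 0.16 × 0.952 × 26 = 4.0 points.

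The 5%/20% row expects 1.25 retrieved values per arm, so the fallback would probably apply there and the shift would not arise. The 10%/20% row (2.5) is at the edge of the trigger. The rows that set the ends of the range, 0.34 and 2.13, expect more than two.

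Unequal discontinuation changes the picture. With 10% on tralokinumab, 20% on placebo, r = 20% and q = 0, the net shift is 0.08 × 0.978 × 26 − 0.16 × 0.952 × 12 = 2.03 − 1.83 = 0.2 points. With 5% vs 20% it is 0.04 × 0.990 × 26 − 1.83 = −0.8. If off-drug response equals on-drug response in each arm, it is zero.

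**The case against.** The strongest reply is that 14.3.9 only swaps one building block. The EASI block in 14.3.8.4 is also worded for two groups by arm under MAR, yet 14.3.8.3 uses it inside a four-group structure. On that reading the IGA block replaces the EASI block and the four groups stay. Panel 13 supports this, and so does the SAP, whose 6.6.2 refers to discontinued subjects in each arm and whose 6.8.5 has an indicator separating discontinuation from COVID-19 onset for treatment policy. This is a fair reading, so the texts are in conflict rather than settled. It does not remove the gap: 14.3.9 names the tertiary estimand explicitly, and even on the favourable reading there is no IGA model for discontinued subjects.

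Four stronger inferences are not supported:

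- *The SAP confirms two groups.* The sentence "Imputation will be performed within treatment groups at each visit" stands in a paragraph on merging sparse IGA categories. It explains why categories may be merged in one group and not the other, and is compatible with four groups.
- *Discontinued subjects are imputed as if still on drug, as under the hypothetical estimand.* That estimand discards data after discontinuation and rescue. Here retrieved off-drug values enter the model, rescue is ignored, and imputation conditions on the subject's own earlier IGA values. Donors are mostly, not only, on-drug.
- *The bias can be read from arm-level products.* For example, 10% discontinued × 90% missing × a 20-point gap = 1.8 points. That case leaves 125 × 0.10 × 0.10 = 1.25 retrieved per arm, so the fallback would be expected to make those subjects non-responders, and an arm-level figure is not the shift in the difference.
- *The IGA tests are compromised.* Section 14.3.6 bases testing on the primary estimand, where discontinuation without prior COVID-19 onset is non-response.

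**Conclusion.** The conflict is real and should be resolved before unblinding. Section 14.3.9 assigns a two-group IGA imputation to the treatment-policy estimand, against 14.3.8.3 and Panel 13, and the SAP leaves it open. The literal rule does not estimate what the estimand names.

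The consequence is confined to supportive IGA 0/1 results. The illustrated inflation of the risk difference is about 0.3 to 2.1 percentage points. It rests on phase 2b Week 12 rates, assumed discontinuation (equal in both arms) and retrieval, a common off-drug rate, and a mixture that ignores covariates and earlier visits. It is zero if off-drug and on-drug response are equal, and it can shrink or reverse if placebo subjects discontinue more often. Where the fallback applies, the effect does not arise.

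**What to change.** State in the SAP (6.6.3.1 or 6.6.4), as a clarification of Protocol 14.3.9:

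1. The two-group IGA algorithm applies to the primary and quaternary estimands.
2. For the tertiary estimand, the stepwise ordinal model is run within each arm in not-discontinued subjects only. Subjects whose first event is COVID-19 onset stay in this group, as Panel 13 has it.
3. Discontinued subjects with missing IGA are imputed at Week 16/26 by an ordinal model with prior CSA use and baseline IGA, fitted to retrieved IGA values of discontinued subjects in the same arm. If the data are too sparse for both factors, drop prior CSA use first, following the order in 14.3.8.3.
4. The SAP 6.6.2 fallback applies to IGA 0/1 at Week 16 and at Week 26.

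The cost is a short SAP clarification and minor programming. Imputation for discontinued subjects becomes less precise, because few retrieved values are expected.

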14.3.9.1 Primary estimand for the continuous secondary endpoints: ‘hypothetical’

The primary estimand for the continuous secondary endpoints will be:

- Treatment difference in change from baseline to Week 16/ Week 26 in SCORAD and DLQI scores, respectively, if all subjects adhered to the treatment regimen in the sense that they did not discontinue IMP permanently, no rescue treatment was made available, and as if the COVID-19 pandemic did not happen before Week 16/ Week 26.

The primary estimand assesses the expected benefit when adhering to the treatment regimen tralokinumab+TCS with no rescue treatment or subject-onset of the COVID-19 pandemic as compared to a treatment regimen with placebo+TCS with no rescue treatment or subject-onset of the COVID-19 pandemic.

Primary analysis of the primary estimand (continuous secondary endpoints)

Data collected after permanent discontinuation of IMP, after initiation of rescue treatment, or after subject-onset of the COVID-19 pandemic will not be included in the analysis (Panel 13).

The endpoints will be analysed using a repeated measurements model on the post-baseline responses up to Week 26 with an unstructured covariance matrix, Kenward-Roger approximation to estimate denominator degrees of freedom, and the mean modelled as follows (shown for change from baseline in SCORAD):

Change from baseline in SCORAD

$$= \text{treatment} \times \text{visit} + \text{baseline SCORAD} \times \text{visit} + \text{prior CSA use} + \text{country} + \text{baseline IGA}$$

This model assumes that data is MAR within each treatment group. The estimates will be presented with nominal p-values and 95% CI at each visit. The comparisons between tralokinumab+TCS and placebo+TCS will be at Week 16 and Week 26.

Sensitivity analysis for the primary estimand (continuous secondary endpoints)

Rather than assuming that observations are MAR within each treatment group it is assumed that missing data from subjects who had any of the intercurrent events in the tralokinumab+TCS group will resemble data from subjects from the placebo+TCS group who had none of the intercurrent events. Imputation of missing data at Week 16/ Week26 will be done using a pattern mixture model where missing data in the tralokinumab+TCS group as well as the placebo+TCS group will be imputed from the placebo+TCS group (using a so-called copy-reference approach). The procedure for the change from baseline in SCORAD at Week 16/ Week 26 is described below. The same procedure will be applied for the DLQI endpoint.

1. Intermittent missing values will be imputed in each group using a Markov Chain Monte Carlo method to obtain a monotone missing data pattern, and 100 copies of the dataset will be generated (seed=14563746).
2. For each of the 100 copies of the dataset, an ANCOVA model will be fitted to the SCORAD value at Week 2 in the placebo+TCS group. The model will include effects of baseline SCORAD as a covariate with prior CSA use (yes/no), country

- (Germany: yes/no), baseline disease severity (IGA 3 or 4) as factors. The estimated parameters, and their variances, will be used to impute missing values at Week 2 for the placebo+TCS group as well as the tralokinumab+TCS group (seed=65749346).
3. For each of the 100 copies of the dataset, missing values at Week 4 will be imputed in the same way as for Week 2. The imputations will be based on a similar ANCOVA model, but with SCORAD value at Week 2 included as an additional covariate. The parameters from the model will be estimated based on data from the placebo+TCS group. The estimated parameters, and their variances, will be used to impute missing values at Week 4 for both treatment groups.
 4. This stepwise procedure will then be repeated sequentially for the remaining visits starting with Week 6 until Week 16 (or Week 26 for the Week 26 endpoint) with the SCORAD values from the preceding 2 visits included as covariates in addition to baseline SCORAD as a covariate, prior CSA use, country, and baseline disease severity as factors.

For each of the 100 imputed dataset, the change from baseline in SCORAD at Week 16/ Week 26 will be analysed using an ANCOVA model with effects of treatment, prior CSA use, country, baseline disease severity, and baseline SCORAD value as factors. The estimated difference at Week 16/ Week 26 will be derived together with the associated standard error. The estimates and standard errors from the 100 analyses are pooled to one estimate and associated standard error using Rubin's rule to draw inference. From these pooled estimates, the 95% CI for the treatment difference will be calculated.

14.3.9.2 Secondary estimand for the continuous secondary endpoints: 'treatment policy'

The secondary estimand for the continuous secondary endpoints will be:

- Treatment difference in change from baseline to Week 16/ Week 26 in SCORAD and DLQI scores, respectively, between tralokinumab+TCS and placebo+TCS regardless of rescue treatment use and treatment discontinuation, as if the COVID-19 pandemic did not happen.

The secondary estimand assesses the average difference in change from baseline in SCORAD and DLQI at Week 16/ Week 26, resulting from initiation of a treatment regimen with tralokinumab+TCS and rescue treatment as compared to a treatment regimen with placebo+TCS and rescue treatment.

Primary analyses for the secondary estimand (continuous secondary endpoints)

Data retrieved at Week 16/ Week 26 for subjects who prior to Week 16/Week 26 have permanently discontinued IMP for other reasons than the COVID-19 pandemic will be included in the analysis.

For subjects who have subject-onset of the COVID-19 pandemic prior to Week 16/ Week 26 and prior to any permanent discontinuation of IMP not due to the COVID-19 pandemic, any observed data from these subjects will be ignored and treated as missing in the same manner as missing data from not discontinued subjects in the analysis ([Panel 13](#)).

Missing Week 16/ Week 26 data will be imputed using multiple imputations assuming that data is MAR within the groups used for imputation.

Imputation of missing data at Week 16/ Week 26 will be done using multiple imputations within 4 groups defined according to randomised treatment group and whether or not subjects have discontinued treatment prior to Week 16/ Week 26. Within a given treatment group, retrieved data from discontinued subjects will be used to impute missing data for other discontinued subjects. Similarly, the available data from not discontinued subjects will be used to impute data for such subjects where the Week 16/ Week 26 value is missing/treated as missing.

For not discontinued subjects, the stepwise multiple imputations procedure will be conducted in the same way, using the same seeds, as specified for the imputation of the underlying EASI values in the primary analysis of the quaternary estimand for the binary endpoints (see [Section 14.3.8.4](#)).

For discontinued subjects, it is expected that the number of subjects with retrieved data at Week 16/ Week 26 will be too small to facilitate the same imputation model as mentioned just above. Consequently, an imputation model with prior CSA use (yes/no), country (Germany: yes/no), and baseline disease severity (IGA 3 or 4) as factors and baseline SCORAD/DLQI as a covariate will be applied for discontinued subjects. Some factors may have to be omitted, depending on the observed data, e.g. all subjects have the same baseline disease severity. In that case, the preferred order of elimination of the effects from the imputation model will be: country, prior CSA use, baseline disease severity, and baseline SCORAD/DLQI (seed=12576546).

Each of the 100 imputed datasets will be analysed as described in the sensitivity analyses for the primary estimand for the continuous secondary endpoints (see [Section 14.3.9.1](#)).

Sensitivity analyses for the secondary estimand (continuous secondary endpoints)

Rather than assuming that observations are MAR, it is assumed that missing data from subjects in the tralokinumab+TCS group who have/have not discontinued treatment prior to Week 16/ Week 26 will resemble data from subjects from the placebo+TCS group who have/have not discontinued treatment prior to Week 16/ Week 26.

Imputation of missing data at Week 16/ Week 26 will be done using a pattern mixture model where missing data in the tralokinumab+TCS group as well as the placebo+TCS group will be imputed from the placebo+TCS group (copy-reference approach). With this exemption, the MI procedure and analysis will be conducted in the same way as described for the primary analysis of the secondary estimand for the continuous secondary endpoints (Section 14.3.9.2).

**14.3.9.3 Tertiary estimand for the continuous secondary endpoints:
'COVID-19 modified composite'**

The primary estimand for the continuous tertiary endpoint will be:

- Treatment difference in change from baseline to Week 16/Week 26 in SCORAD and DLQI scores, respectively, without rescue treatment and treatment discontinuation, as if the COVID-19 pandemic did not happen

The continuous tertiary estimand assesses the expected treatment difference (obtained without initiation of any rescue treatment and/or permanent discontinuation of IMP) after 16/ 26 weeks, resulting from initiation of a treatment regimen with tralokinumab+TCS compared to a treatment regimen with placebo+TCS.

Primary analysis for the tertiary estimand (continuous secondary endpoints)

Data retrieved at Week 16/ Week 26, depending on the endpoint, for subjects who have received rescue treatment or permanently discontinued IMP prior to the visit, without subject-onset of the COVID-19 pandemic, will be considered non-responders by using worst observation carried forward (including the baseline value) (Panel 13).

Any missing or collected data from subject who have subject-onset of the COVID-19 pandemic as their first prior intercurrent event will not be used, but instead be imputed assuming MAR following the start of subject-onset of the COVID-19 pandemic.

Any data missing at the relevant visit from subjects without prior rescue treatment, permanent discontinuation of IMP, or subject-onset of the COVID-19 pandemic will be imputed assuming MAR.

The procedure for imputing values according to the rules described above will follow the same imputation procedure described in the primary analysis of the binary primary estimand. However, any data missing at the relevant visit from subjects without a prior intercurrent event will not be imputed as a ‘non-responder’ after the imputation step, but will be imputed assuming MAR.

For each of the resulting 100 imputed datasets, this primary analysis will be analysed using an ANCOVA model with effects of treatment, prior CSA use (yes/no), country (Germany: yes/no) and baseline disease severity (IGA 3 or 4) as factors. The estimates and standard errors from the 100 analyses are pooled to one estimate and associated standard error using Rubin’s rule to draw inference. From these pooled estimates, the 95% CI for the treatment difference will be calculated.

